9.3 Study Records

9.4 Use of Information and Publications

10. References

Couple-Based Motivational Interviewing with Mobile Breathalyzers to Reduce Alcohol Use in South Africa

Study Investigators

[name]

Principal Investigator

Center for AIDS Prevention Studies

University of California, San Francisco

[name], PhD

Site Principal Investigator

Human and Social Development Programme

Human Sciences Research Council

[name]

Co-Investigator

Department of Psychology

Hunter College, City University of New York

[name]

Co-Investigator

Center for AIDS Prevention Studies

University of California, San Francisco

[name]

Co-Investigator

Center for AIDS Prevention Studies

University of California, San Francisco

Couple-Based Motivational Interviewing with Mobile Breathalyzers to Reduce Alcohol Use in South Africa

SCHEMA

Design: Formative qualitative phase followed by pilot randomized controlled trial

Population: Heterosexual couples with at least one heavy alcohol drinker on antiretroviral therapy

Study size: 40 key stakeholders and 90 couples/180 individuals (220 people total)

Study duration: 36 months

Aim 1: To develop a couple-based Motivational Interviewing intervention with mobile breathalyzer technology to deliver real-time feedback on blood alcohol content (BAC) levels. We will target heavy alcohol users with HIV and enroll their primary partner.

Aim 2: To develop and pilot test the study procedures for a future randomized controlled trial (RCT) of the couple-based intervention. We will develop and pilot test: a) training procedures; b) randomization procedures; c) the pilot study procedures; and d) data collection instruments.

Aim 3: To determine the feasibility and acceptability (F&A) of couple-based MI as a standalone intervention and when combined with mobile breathalyzers with couples to provide real-time feedback and support.

Study Site: Vulindlela/Sweetwaters community, KwaZulu-Natal, South Africa

1.0 INTRODUCTION

In sub-Saharan Africa (SSA), alcohol use is described as “adding fuel to the fire” for people living with HIV (PLWH)[1], threatening the success of HIV treatment programs and progress towards UNAIDS goals.[2-5] Our research in SSA suggests that primary partners are key to the success of alcohol interventions given their critical role in helping drinkers reduce alcohol use and the couple dynamics that intersect with alcohol use.[6-9] Harnessing this powerful form of social support is critical in a setting where clinical services for alcohol misuse are inadequate and can be costly for patients. One approach that has been effective at reducing alcohol use among PLWH is motivational interviewing (MI) that incorporates mobile technology for real-time feedback.[10-17] MI is a collaborative, goal-oriented style of communication with particular attention to the language of change. It is designed to strengthen personal motivation for and commitment to a specific goal by eliciting and exploring the person’s own reasons for change within an atmosphere of acceptance and compassion.

In this study, we propose to develop and test a couple-based MI intervention with mobile breathalyzer technology to provide dyadic support around drinking for HIV-affected couples in KwaZulu-Natal, South Africa.

Few couple-based MI approaches have been developed for alcohol use, particularly in the African context. In the US, there is evidence that couple-based MI is feasible, acceptable, scalable, and efficacious at reducing substance use.[9, 18-20] In studies with individuals, daily monitoring of drinking levels, when paired with MI, has a greater effect on drinking than MI alone[15-17] and we hypothesize that monitoring may have additional benefits with couples. Although primary partners are generally aware of a drinker’s alcohol use, they have inaccurate knowledge of drinking amounts and frequency, in part, because drinking often occurs in gender-segregated spaces in SSA. Accurate knowledge of drinking levels in real-time is critical to trigger couple communication, and timely and tailored social support. Mobile breathalyzers have been shown to be a feasible and acceptable strategy for self-monitoring alcohol use in studies with individuals[21-23] and new products have been developed for dyads that share blood alcohol content (BAC) levels with support partners via a mobile app. Our scientific premise is that mobile breathalyzers to provide real-time feedback and support can be synergistic with a couple-based MI approach that fosters couple communication and problem-solving skills to effectively engage with the breathalyzers and work together to reduce alcohol use. We hypothesize that this combination will have a greater effect on drinking reductions than couple-based MI alone.

2.0 Study objectives and Design

2.1 Intervention Feasibility

Preliminary data to support proposed intervention: Couple-based MI interventions for substance use have demonstrated feasibility, acceptability and preliminary efficacy. Co-I [name] developed a couple-based MI intervention with US male couples called *We Test* to enhance the effectiveness of couples HIV testing and counselling (CHTC) by including structured components to address substance use and couple communication skills. The RCT findings showed that completion of a substance use module led to immediate decreases in drug use, and when combined with training in couple communication, resulted in reductions in drug use at 3- and 6-month follow-up.[19] Co-I [name] also developed a three-session MI-based intervention with US male couples to reduce HIV risk and drug use (*Couples Health Project*).[19, 20] A pre-pilot RCT of the intervention prototype with 20 couples showed that: 1) 19 out of 20 couples completed all three MI sessions; 2) retention was high at 1-month (95%) and 3-month (93%) follow-up; 3) and couples found the intervention highly acceptable. In the pilot RCT that followed, the intervention significantly reduced drug use at the 3-month follow-up among participants with high levels of baseline drug use.[20] We acknowledge that US male couples and those in South Africa may differ (e.g., higher rates of IPV and heavy drinking in South Africa), which our adaptation plan will take into account.

Our team's research in KZN suggests that a technology-based intervention will be feasible. In South Africa, smartphone penetration rates are high (82%) and of all provinces, KZN has the second highest number of 4G/LTE subscribers.[24] Mobile phones have been successfully incorporated into interventions in South Africa and elsewhere in the region.[25-27] Multiple studies at the proposed site have demonstrated the feasibility of digital interventions in HIV care. Site PI [name] demonstrated the feasibility of using an mHealth system to improve linkage-to-care after home-based testing[28] and a conversational agent (chatbot) to provide counselling for HIV self-testing.[29] These studies rely on high smartphone penetration rates and a strong mobile network. Pilot data from 2016 with PLWH in KZN (n=101) found that 96% of participants reported using a cell phone.[28] The research area is serviced by a strong network of mobile phone towers and in speed tests conducted at 14 sites spanning a distance of 60 km, we achieved an average download speed of 22.6 Mbps (3.5– 54.5 Mbps) and upload speed of 6.2 Mbps (0.05–14.2 Mbps). Although network conditions vary, speed tests show that we will have ample bandwidth to use the mobile breathalyzer technology for this study.

2.2. Aim 1

In the first phase (months 1-12), we will adapt our team's interventions to address alcohol use in South African couples living with HIV and incorporate the mobile breathalyzers.

2.3. Aim 2

As part of the first phase, we will develop the intervention manual, training procedures, randomization procedures, implementation procedures, and data collection instruments for the pilot RCT.

2.4 Aim 3

In the second phase (months 13-36), we will recruit 90 couples who will be randomized to a control arm, couple-based MI arm, and couple-based MI plus mobile breathalyzers arm. Couples will be assessed at baseline, , 2, and 6-months post intervention initiation and a subsample of 15

Couple-Based Motivational Interviewing with Mobile Breathalyzers to Reduce Alcohol Use in South Africa

couples will complete exit interviews. In months 31-36, we will analyze the F&A data, discuss the findings as a team, and identify modifications to the intervention in preparation for a future trial.

2.5 Study design

For Aim 1, we will adapt a couple-based MI framework and interventions developed by co-I [name] (*We Test* and the *Couples Health Project*) to address alcohol use in heavy alcohol users and their primary partners and incorporate the mobile breathalyzer component. We will follow the ADAPT-ITT framework by conducting focus group discussions (FGDs) with around 40 key stakeholders to gain feedback on the intervention and then refining the intervention. For Aim 2, we will develop training procedures, study procedures, and data collection instruments that will be pilot tested during the RCT. For Aim 3, we will conduct a three-arm RCT with 30 couples randomized to the following arms (90 couples total): 1) an enhanced usual care control condition; 2) couple-based MI; and 3) couple-based MI with mobile breathalyzers for real-time feedback. For arm 2 and 3, couples will receive 3 MI sessions over a 60-day period with an experienced counselor to help strengthen communication and problem-solving skills around alcohol use. For Arm 3, couples will use the mobile breathalyzers and app for 60 days and receive the same MI sessions, which will also incorporate feedback on BAC levels (prior 30 days) and teach couples how to effectively engage with the breathalyzers. This design will allow us to assess the effectiveness of couple-based MI alone and the added synergistic effect of the mobile breathalyzers on alcohol use and HIV outcomes (e.g., adherence to antiretroviral therapy (ART), viral suppression). Our F&A outcomes will include enrollment and retention rates, satisfaction with both intervention arms, MI session attendance rates, and follow-up survey completion rates. We will also conduct qualitative interviews with a subset of 15 couples to contextualize F&A data and refine the intervention and procedures for a future full-scale efficacy trial.

3.0 Study Population

3.1. Couple Eligibility

Inclusion criteria:

- (1) In a primary relationship for at least six months
- (2) Aged 18-49
- (3) Have at least one partner (the “index patient”) with a positive AUDIT-C screen (score of 4 for men and 3 for women; prior 3 months) and on ART for at least six months (a time when alcohol use is found to rebound) who has disclosed their HIV status to their partner in the study
- (4) Both partners separately agree to participate in the study for the couple to be enrolled.

Exclusion criteria:

We will exclude participants with an AUDIT-C score greater than 12, indicating risk of severe alcohol use disorder. Participants with severe drinking issues may not benefit from a brief counseling-based intervention and may need more intensive treatment than our study can provide.

Considering the intervention has a technology component and there may be a difference in acceptability between younger/older participants, we will impose an upper age limit of 49 (an age in which smartphone ownership and internet connectivity drops off in South Africa). We will not exclude those without phones or with incompatible phones to avoid widening the digital divide and excluding those who could really benefit from the intervention. We have budgeted for

Couple-Based Motivational Interviewing with Mobile Breathalyzers to Reduce Alcohol Use in South Africa

phones to be provided. Our intervention may not be appropriate for couples experiencing severe IPV. We will exclude those who fear for their safety by participating in the study and/or report severe IPV in the past 3 months using the WHO measure for South Africa, which assesses physical, sexual, and emotional violence, and determines whether it is mild, moderate, or severe. The WHO measure for IPV contains 8 questions that assess perpetration and victimization of 4 types of severe violence including physical (kicking, punching, hitting, beating, scalding, burning), threats using weapons such as a gun or a knife, and restraint (i.e. holding down) in the past three months. The WHO questions on IPV will be administered to both members of the couple. Couples-based interventions in South Africa have successfully employed this approach. We believe this approach balances sample generalizability with safety. If couples report any IPV (mild, moderate, or severe) during screening or over the study, we will follow an established protocol to assess safety, provide emotional support, and provide intervention and/or linkage to psychological and/or medical services. If either person in the couple declines to participate, the couple as a whole will be ineligible.

[name] prior work with couples in this community in KZN showed that less than 1% of female partners reported any alcohol use, with the primary drinker almost always being the male partner. As such, we will not exclude dual-drinking couples since these couples could really benefit from the intervention. However, should we enroll couples with two heavy alcohol drinkers, our couple-based MI approach is designed to be flexible to handle cases where both partners are heavy drinkers, and will consider change behavior in both partners. The software for the breathalyzer is not optimized for both partners being "testers" and "accountability partners." Therefore, in couples with two qualified drinkers, whichever one is screened first will be considered the "index patient" and get the breathalyzer. In couples with two heavy drinkers on ART, both partners will have blood draws for viral load and/or alcohol use at follow-up visits.

3.2. Recruitment Process

Aim 1: For the two FGDs with couples (3-4 couples per group), we will recruit couples using procedures from our prior studies with couples in South Africa and Malawi. A team of recruiters will approach index patients at HIV clinics while waiting to attend appointments. We will announce the study during the daily health information talks in the waiting rooms and interested patients can approach the recruiters. If the patient is interested and eligible, we will provide them with a study information card to give their primary partner and will set up a phone appointment to screen the partner. If both partners are interested and eligible, the couple will be invited for a secondary screening to verify that the partnership is legitimate (e.g., confirming partner names, relationship length, etc.). To ensure we capture primary partnerships, both partners will be asked, "Of all your romantic partners, who are you the closest with?" Screenings will be interviewer-administered using tablet devices. If the couple remains eligible, both partners will provide written informed consent and be invited to participate. Partners will be consented separately to ensure a lack of coercion. Couples who are ineligible will be informed that they are ineligible but will not be given a specific reason why (i.e. which eligibility criteria they did not meet). Recruiters may deflect questions about eligibility by saying, "the computer program determines eligibility but does not provide a specific reason." Similarly, couples who are ineligible because one or the other does not want to participate will not be informed that this is the reason for ineligibility to avoid disclosing each partner's decision to provide consent.

Couple-Based Motivational Interviewing with Mobile Breathalyzers to Reduce Alcohol Use in South Africa

Couples may also be identified from previous or current studies who have consented to be contacted for other research studies, and through our community partners and associated HIV testing/care services.

For the three FGDs with stakeholders (6-8 per group), which will consist of HIV care providers (nurses, clinic volunteers, clinicians), community representatives and religious leaders who interact with couples who drink, and alcohol vendors (e.g., shebeen owners, local brewers), we will recruit them using our professional networks in this region of KZN.

Aims 2 and 3: We will recruit couples using a combination of community-based and clinic-based recruitment approaches. Index patients who are heavy drinkers on ART for at least 6 months will be targeted first, followed by their primary partner. We will recruit around 120 couples to achieve the desired sample size of 90 couples (180 individuals). This assumes we will lose around 25-30% after randomization based on other studies at this site.

We will use a combination of active and passive recruitment strategies to enroll the sample.

Community-based recruitment: Index patients will be identified through community-based organizations or through locations in the community where drinkers can be found. Recruiters will use procedures established at HSRC to identify and recruit participants using a community mobilization approach. Individuals and couples will be targeted by a team of recruiters, who will approach potential participants in public areas in the community, such as alcohol venues (e.g., shebeens, bottle shops), markets, sports grounds, taxi ranks, HIV clinics, and community events. Recruiters will target couples together if possible, although our other studies have shown that couples are not often together in public. Potential participants will also be recruited passively (i.e., through fliers in the community). These fliers describe the study and invite interested individuals to contact the project staff by calling or sending a free “call me” SMS to the telephone number listed. Recruiters will return these messages as soon as possible and no later than the next working day.

Clinic-based recruitment: We will also actively recruit index patients at HIV clinics during morning health talks when patients are attending appointments. Recruiters will screen index patients in the waiting rooms immediately following the talks or distribute fliers/information cards so interested patients can later contact the study team if interested. We will also passively recruit index patients using fliers placed at the clinics. Clinic-based outreach teams and care providers will also help to identify HIV patients who are heavy alcohol drinkers and on ART for at least six months and refer patients to the HSRC recruiters.

Recruitment from other studies: There are other studies at the HSRC site that may be able to refer participants to the study team, for example, if they were ineligible for another study but may be interested in participating in research.

In either approach, recruiters will ask potential participants if they would like to hear about the study and explain the nature of the study using standard recruitment scripts.

If the index patient is interested and eligible, we will provide them with a study information card to give their primary partner and will set up a phone appointment to screen the partner. If both partners are interested and eligible, the couple will be invited for a secondary screening to verify that the partnership is legitimate (e.g., confirming partner names, relationship length, how the

Couple-Based Motivational Interviewing with Mobile Breathalyzers to Reduce Alcohol Use in South Africa

couple met) and assess the risk for violence by participation in the study. To ensure we capture primary partnerships, both partners will be asked, “Do you have a primary partner, meaning a person who you are committed to above anybody else and with whom you have had sexual relations?” Screenings will be interviewer-administered using tablet devices either in-person or via phone. If the couple remains eligible and is a legitimate couple, both partners will provide written informed consent and be invited to participate. Partners will be consented separately to ensure a lack of coercion.

3.3. Participant Retention

Aim 1 requires only a single interaction with participants. The intervention period for Aim 2 and 3 will last 60 days with assessments at baseline, 2-months and 6-months post intervention initiation. Upon enrollment, we will obtain contact information (e.g., two cell phone numbers, directions to households, and contact information for up to three other individuals) to facilitate tracking. For the pilot study in Aim 3, participants will also be provided with phones allowing us the capability to reach them via SMS or calls as an alternative to their main phone number. Participants will be contacted regularly (e.g., twice a month) to update contact information and check on location. Prior to the assessment visits, reminder calls and SMS messages will be made to both partners one week before the appointment and again 1-2 days prior. For participants who miss appointments, we will limit the number of phone call attempts to 3-4 to respect privacy and the right to refuse. There may be special circumstances when outreach workers will be dispatched to participants’ homes (with their prior consent) such as when calls do not go through.

We anticipate that we will lose a very small percentage of couples due to break-ups, deaths, and migration (<5% in another study at the site called *Uthando Lwethu*), which we have accounted for in recruitment and analysis plans. One assessment will be conducted with each partner separately following the break-up to understand when the couple broke up, whether study participation contributed to the break-up, and if not, other reasons for why the couple broke-up. The breakup assessment will also allow us to identify any negative effects of participation on couples. If the study contributed to the break-up or the break up was a negative experience, we will follow the adverse event logging process. We will continue to follow each partner individually and administer study assessments given that our study outcomes (e.g., alcohol use) are at the individual level. This will allow us to explore whether participation in the intervention, despite the break-up, still had an effect on their alcohol use. However, couples who break-up before participation in the intervention will exit the study.

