5.7 Recruitment and retention. We will recruit and randomize around 120 couples to meet our target sample size of 90 couples, assuming that we will lose around 25-30% of couples after randomization. We anticipate that we will lose a very small percentage of couples due to break-ups, deaths, and migration (<5% in Uthando Lwethu), which we have accounted for in recruitment and analysis plans.

5.8 Randomization process. After informed consent and the baseline assessment, couples will be randomized to either the control arm, the couple-based MI arm, or the couple-based MI with

Couple-Based Motivational Interviewing with Mobile Breathalyzers to Reduce Alcohol Use in South Africa

mobile breathalyzers arm (MI *Plus*). We will use randomly permuted block sizes (e.g., 3, 6, and 9) generated using a computerized and secure process. The UCSF project coordinator and the HSRC data manager will use the table that the statistician created to print documents that assign participants to one of the three arms. These documents will be placed in sealed envelopes and maintained by the HSRC data manager. HSRC interviewers will take a small subset of envelopes into the field with them. At the end of the baseline survey, the index patient will be given the envelope that contains the random assignment. Couples will receive an appointment card with a date for their next study visit following randomization.

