6.0 Safety monitoring and adverse event reporting

6.1. Safety monitoring

Safety-related risks could consist of: 1) loss of confidentiality; 2) loss of privacy; 3) couple tension, conflict and/or violence, and coercion; 4) discomfort or distress as a result of the personal and sensitive nature of the interviews or intervention sessions on alcohol, relationship dynamics, and violence; and 5) risks associated with finger pricks to collect blood samples for viral load and alcohol biomarkers (Phosphatidylethanol, or "PEth").

Any incidents involving subject safety will be reported to both institutional IRBs (Human Sciences Research Council and The University of California, San Francisco by the PI within 10 working days. The following information will be included in any report: 1) all serious adverse events associated with study procedures and/or 2) any events or problems involving the conduct of the study or patient participation, including problems with the recruitment or consent processes. The US PI will also provide a description of any problems or issues observed in the course of the study to each IRB on an annual basis.

Safety monitoring procedures. All safety-related risks will be monitored routinely at the time of assessment or intervention sessions. Procedures are in place to protect the confidentiality of information from one's partner and to monitor any confidential information. Interviewers and intervention staff will be trained to increase their sensitivity and present a caring and non-threatening manner regarding topics such as sexuality, HIV, and relationship issues. At any sign of discomfort or distress, or by request, interviews will be stopped. Confidentiality will be assured to participants at the time of consent, and they will be assured their answers or responses cannot be used against them for any reason, or for denial of any medical treatment. Standardized procedures will be documented and reviewed with staff regarding the possibility of tension, conflict or violence between partners. Procedures will be in place to monitor and respond to any instances reported by the participants of any type of negative relationship event, and proper action will be taken, including staff intervention and/or provision of referral for services depending on the level of the event (e.g., relationship conflict, an episode of domestic violence,

Couple-Based Motivational Interviewing with Mobile Breathalyzers to Reduce Alcohol Use in South Africa

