8.0 Human Subjects Considerations

8.1 Ethical Review

The study protocol, informed consent forms, and other requested documents — and any subsequent modifications — will be reviewed by the Human Sciences Research Council Research Ethics Committee in South Africa, and the Institutional Review Board at the University of California, San Francisco. Subsequent to initial review and approval, the responsible IRBs/ECs will review the study at least annually.

Each site Investigator will make safety and progress reports to the IRBs/ECs at least annually, and within three months after study termination or completion. These reports will include the total number of participants enrolled in the study, the number of participants who completed the study, all changes in the research activity, all SAEs, and all unanticipated problems involving risks to human subjects or others.

The results of all DSMB reviews of the study also will be provided to the IRBs/ECs.

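### Section 3.3 logs a break-up as an adverse event only after an undefined judgement made with the arm known, and no count of all break-ups by arm is planned

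*Combined protocol and SAP*

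**What the plan says.** Section 3.3 (Participant Retention) contains four relevant statements.

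- Ascertainment: "One assessment will be conducted with each partner separately following the break-up to understand when the couple broke up". The same assessment asks whether taking part in the study played a role and, if not, what did. It carries no condition on arm or cause.
- Entry to the adverse event log: "If the study contributed to the break-up or the break up was a negative experience, we will follow the adverse event logging process".
- Early separations: "couples who break-up before participation in the intervention will exit the study". Couples who separate later are followed as individuals.
- Expected frequency: the investigators expect to "lose a very small percentage of couples due to break-ups, deaths, and migration (<5% in another study at the site" (the text goes on to name that study).

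Section 5.7 plans to "recruit and randomize around 120 couples to meet our target sample size of 90 couples", in three arms. Section 5.8 has the index patient receive the envelope with the assignment at the end of the baseline survey. No blinding of interviewers, counsellors or whoever judges an adverse event is described.

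The measures table in 5.11 lists communication, intimate partner violence and relationship scales among the secondary outcomes, but not dissolution of the relationship. Table 4 in 7.2 reports retention and reasons for dropout. Section 7.3 names no analysis of break-ups.

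**The concern.** Break-up is a plausible harm of an intervention that brings couples into joint sessions about drinking and, in arm 3, shows one partner the other's breathalyzer readings. The protocol names couple tension and conflict as a risk in 6.1 and 8.3. In 5.14 it asks whether knowing the readings increases conflict.

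The ordinary safeguard for such a harm is to count every event by randomised arm and record the suspected cause separately. Section 3.3 reverses this: for the adverse event log, a judgement comes first and the count follows. What counts as a contribution by the study, or as a negative experience, is left open. Couples who have had counselling sessions or shared readings have more study activity to which they can attribute a separation than couples who had 5 to 10 minutes of brief advice. Two arms with the same true break-up rate could then show different logged counts, and a true excess could be blurred.

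The exit rule adds a second filter after randomisation. Control counselling is given after randomisation (5.9), while the first motivational interviewing session may fall up to two weeks after baseline (4.0). The period in which a separation counts as preceding the intervention may therefore be longer in arms 2 and 3.

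**Working it through.** The plan gives no figure for break-ups alone, so there is none to reproduce. The check has two parts.

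**1. Does any other provision supply an unfiltered count by arm?**

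- Break-up assessment (3.3): records date and reasons for each case, but no section says the results will be tabulated by arm.
- DSMB (6.3): receives all adverse event reports and reviews all accrued data. A break-up that fails the 3.3 test is not an adverse event report. It could reach the DSMB as accrued data, but no break-up table is specified.
- Retention row of Table 4 (7.2): covers dropouts. Separated partners are still followed, so a break-up need not be a dropout.
- Outcomes (5.11) and hypotheses (7.3): include violence and relationship scales. These are related to break-up but are not the same event.

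None of these is a planned count of all break-ups by arm.

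**2. How many events are at stake?**

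Inputs: 90 couples (target) or 120 (randomised), three arms, and a ceiling of 5% that pools break-ups, deaths and migration (3.3, 5.7). Formula: events = couples × 0.05; per arm = events / 3.

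- 90 couples: 90 × 0.05 = 4.5; 4.5 / 3 = 1.5 per arm of 30.
- 120 couples: 120 × 0.05 = 6; 6 / 3 = 2 per arm of 40.

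These are upper figures for break-ups if the earlier study's rate carries over, because deaths and migration are included.

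To show how sensitive such counts are, assume a true break-up rate of 5% in both arms and different shares of break-ups logged. The shares are assumptions and do not come from the documents. With n couples per arm and share s logged, expected logged count = n × 0.05 × s, and the chance that none is logged = (1 − 0.05 × s)^n.

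| n per arm | Share logged, control / intervention | Expected logged | Chance of none logged |
|---|---|---|---|
| 40 | 100% / 100% | 2.0 / 2.0 | 13% / 13% |
| 40 | 50% / 100% | 1.0 / 2.0 | 36% / 13% |
| 40 | 25% / 75% | 0.5 / 1.5 | 60% / 22% |
| 30 | 100% / 100% | 1.5 / 1.5 | 21% / 21% |
| 30 | 50% / 100% | 0.75 / 1.5 | 47% / 21% |
| 30 | 25% / 75% | 0.375 / 1.125 | 69% / 32% |

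For example, with n = 40 and s = 0.5: 40 × 0.05 × 0.5 = 1.0 and (1 − 0.025)^40 = 0.36. The table shows what differential logging could do. It is not evidence that it will happen.

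**The case against.** The other side has real force on several points.

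**Break-ups are ascertained whatever the cause.** This stands. Only entry to the log is conditional, so the data for a full count should already exist. What is missing is the commitment to count them.

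**The two logging conditions are alternatives.** A distressing break-up is logged in any arm even if nobody blames the study. This stands, and it rules out an extreme illustration in which no control break-up is ever logged. The filter is partial, but its second limb is still undefined.

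**Relationship harm is measured by other means.** Violence and relationship scales are collected in every arm at each survey visit, whatever the attributed cause. A reader might infer that all harm counts depend on attribution by people who know the arm. The documents do not support that; the point is confined to break-up.

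**Safety reporting is not limited to study-related events.** A reader who stops at "all serious adverse events associated with study procedures" in 6.1 might infer that it is. The same sentence adds "any events or problems involving the conduct of the study or patient participation", 6.2 tracks any adverse event after participation, 6.3 sends all adverse event reports to the DSMB and the ethics boards, and 8.1 requires "all SAEs, and all unanticipated problems involving risks to human subjects or others". Sections 6.1 and 8.1 also describe different reports: prompt incident reports, and those made at least annually and after study end. At most, a wording difference remains to be aligned.

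**The DSMB is not confined to the adverse event log.** Section 6.3 has it review all accrued data, so it would be wrong to say that its benefit-harm review rests only on logged events.

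**A table of so few events cannot settle anything.** This also stands. Two break-ups among 30 couples is 6.7%, with an exact 95% confidence interval of about 1% to 22%. The table is worth having as an unbiased description and for planning the full trial, not as a test.

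**Conclusion.** The point holds in a limited form. Entry of a break-up to the adverse event log depends on two undefined conditions. No unfiltered count by randomised arm is planned, and couples who separate before the intervention leave the study. Logged break-up counts could therefore differ between arms through attribution alone.

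The size is at most about 4.5 to 6 couples overall, or 1.5 to 2 per arm, so one or two discretionary omissions would change the picture. This rests on two assumptions. The first is that the pooled under-5% rate from the earlier study at the site applies here. The second is that those judging know the arm, which is inferred from the envelope procedure and the absence of any blinding text; the protocol does not state it.

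The finding does not extend to violence, to other adverse events or to the scope of serious adverse event reporting. It does not show that the DSMB would be denied the information.

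**What to change.** In 3.3, replace the conditional rule with three requirements.

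1. Record every break-up after randomisation, in every arm, with its date, including those before the intervention starts.
2. Record attribution to the study and whether the break-up was a negative experience as two separate fields. Define both terms and state who completes the fields.
3. Tabulate all break-ups by randomised arm, with 95% confidence intervals, for the DSMB and the final report, labelled as descriptive. Attribution can be shown as a breakdown of that table.

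Optionally, align the wording of item 1 in 6.1 with 8.1 so that both refer to all serious adverse events.

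The cost is a few more log entries and one more table. The assessment that supplies the data is already planned. For couples who separate before the intervention, the text should make clear that the assessment is done, or at least the date recorded, before they exit.
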